The observed variability in clinical response to currently available asthma therapies appears to be related, in part, to distinctive inflammatory phenotypes (Wenzel 2012). In particular, asthma associated with eosinophilic inflammation in the airway (often referred to as eosinophilic asthma) is common (approximately 40% to 60% of asthmatics) with the degree of eosinophilia associated with clinical severity including the risk of asthma exacerbations (Bateman et al 2010, Bousquet et al 1990, Louis et al 2000, Di Franco et al 2003, Scott and Wardlaw 2006, Simpson et al 2006, Zhang and Wenzel 2007). Adjusting conventional ICS-based asthma therapy according to the degree of elevated sputum eosinophils as a marker of disease activity resulted in a reduction in the frequency of asthma exacerbations in prospective trials (Green et al 2002, Jayaram et al 2006). Interleukin-5 (IL-5) is a cytokine factor essential for eosinophil trafficking and survival (Molfinio et al 2011). Clinical trials of neutralizing anti-IL-5 antibodies (mepolizumab and reslizumab) in patients with uncontrolled eosinophilic asthma resulted in an improvement in key asthma control metrics, including asthma exacerbations (Castro et al 2011, Pavord et al 2012). These promising results support continued development of therapies targeting the IL-5 pathway in eosinophilic asthmatics unresponsive to standard therapies.

In contrast to anti-IL-5 therapies, benralizumab (MEDI-563) is a humanized, afucosylated, monoclonal antibody that binds specifically to the human IL-5 receptor alpha subunit (IL-5R $\alpha$ ) on the target cell. The IL-5 receptor (IL-5R) is expressed almost exclusively on the surface of eosinophils and basophils (Takatsu et al 1994, Toba et al 1999). Afucosylation confers enhanced antibody-dependent cellular cytotoxicity (ADCC) which results in highly efficient eosinophil depletion by apoptosis (Kolbeck et al 2012). Single and repeated doses of benralizumab in mild to severe asthma patients during early development or Phase 1/2 development resulted in depletion of blood and airway eosinophils, and improvement in multiple metrics of asthma control including asthma exacerbations, lung function, and Asthma Control Questionnaire (ACQ-6) scores (Busse et al 2010, Gossage et al 2012, Molfinio et al

2012, and Phase 2b MI-CP220 study). For further details please refer to the Investigator's Brochure (IB).

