## 4.1 Screening period

### 4.1.1 Enrolment (Visit 1)

Each potential patient will provide written informed consent, and assent when applicable, prior to any study specific procedures and undergo assessments applicable for the visit (see [Table 1](#)).

Patient must sign the Informed Consent Form (ICF) prior to any other Visit 1 procedures.

Visit 1 assessments are primarily concerned with confirmation of the asthma disease state, the requisite level of severity based on background medications and exacerbation history.

**Source documentation is required for physician-diagnosed asthma, ICS-LABA use (Section 3.1, criterion 5) and asthma exacerbations over the prior year (Section 3.1, criterion 7). A patient verbal history suggestive of asthma symptoms and/or prior asthma exacerbations, but without supporting documentation, is not sufficient to satisfy these inclusion criteria.**

**Examples of acceptable documentation of the asthma disease state and prior asthma exacerbations include clinic visit (primary or specialist Health care provider (HCP)), emergency room/urgent care, or hospital records listing asthma as a current problem, plus documentation of at least 2 asthma exacerbations during the 12 months prior to ICF:**

A qualifying historical asthma exacerbation is a symptomatic worsening requiring systemic corticosteroid (i.e., oral, intravenous (IV) or intramuscular; any healthcare setting or temporary increase from a stable maintenance dose of oral corticosteroid,) or that resulted in hospitalization.

Patients will continue on their current asthma treatment with no changes.

Central laboratory tests for absolute blood eosinophil count will be performed at Visit 1 . Patients who have a blood eosinophil count of  $<300$  but  $\geq 150/\mu\text{L}$  at Visit 1 can be re-tested once. It is recommended that any re-test for blood eosinophils is performed not earlier than 4 weeks from the previous testing; in case of recent treatment with systemic corticosteroids, an interval of  $\geq 6$  weeks from the last dose is recommended.

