### **5.3.3 Healthcare resource utilization**

Broad-based health care utilization asthma related event information will be collected by the Investigator/authorized delegate at each visit (as shown in [Table 2](#)) and recorded in the appropriate eCRF module.

At Visit 1 Healthcare Resource Utilization (HRU) information will be collected with a 1 year recall period. In treatment period, HRU information will be collected with a recall period of ‘since last visit’.

**Note:** Cases of hospitalization after Visit 1 also must be reported as an SAE (see [Section 6.2](#) and [6.4](#)).

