### **8.5.1 Analysis of the primary variable (s)**

The primary efficacy variable is the annual asthma exacerbation rate and the primary analysis is to compare the annual asthma exacerbation rate of benralizumab group with placebo group in patients with baseline blood eosinophil counts  $\geq 300/\mu\text{L}$ .

The null hypothesis is that the exacerbation rate on benralizumab is equal to the exacerbation rate on placebo. The alternative hypothesis is that the exacerbation rate on benralizumab is not equal to the exacerbation rate on placebo, ie,

*H0: Rate ratio (benralizumab vs. Placebo) = 1*

*Ha: Rate ratio (benralizumab vs. Placebo)  $\neq 1$*

Exacerbation rate in the benralizumab group will be compared to exacerbation rate in the placebo group using a negative binomial model. The response variable in the model will be the number of asthma exacerbations over the 48-week treatment period. The model will include covariates of treatment group, region (China/non-China), number of exacerbations in the year before the study, and the use of maintenance oral corticosteroids (yes/no). The logarithm of the follow-up time will be used as an offset variable in the model.

The estimated treatment effect (i.e., the rate ratio of benralizumab versus placebo), corresponding 95% confidence interval (CI), and two-sided p-value for the rate ratio will be presented. In addition, the exacerbation rate and the corresponding 95% CI within each treatment group will be presented.

In addition, the exacerbation rate will also be summarized in patients with baseline blood eosinophil counts  $< 300/\mu\text{L}$ ,  $< 150/\mu\text{L}$ ,  $150\text{-}299/\mu\text{L}$ ,  $300\text{-}449/\mu\text{L}$  and  $\geq 450/\mu\text{L}$  separately.

The individual exacerbation criteria (ER visit due to asthma that required systemic corticosteroids, hospitalization due to asthma, or use of systemic corticosteroids) will also be summarized.

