Change from baseline in asthma symptom total score; day time score, and night time score at Week 48 will be analysed separately using a similar model as the above model for change from baseline in pre-bronchodilator FEV1.

The proportion of patients with  $\geq 1$  asthma exacerbation during the 48 weeks of treatment will be addressed as a supportive variable to the primary objective. The proportion in the benralizumab group will be compared with the proportion in the placebo group using a Cochran–Mantel–Haenszel test controlling for region (China/non-China), number of exacerbations in the year before the study, and the use of maintenance oral corticosteroids (yes/no).

Time to first asthma exacerbation will be analysed as another supportive efficacy variable to the primary objective to explore the extent to which treatment with benralizumab delays the time to first exacerbation compared with placebo. A Cox proportional hazard model will be fitted to data with the covariates of treatment, region (China/non-China), number of exacerbations in the year before the study, and the use of maintenance oral corticosteroids (yes/no).

Annual rate of asthma exacerbations that are associated with an emergency room/urgent care visit or a hospitalization will be analysed using a similar negative binomial model as outlined for the primary efficacy variable in Section 8.5.1.

Change from baseline in total rescue medication use (average puffs/days) and number of nights with awakening due to asthma and requiring rescue medication will be analysed using a similar model as for change from baseline in pre-BD FEV1.

Change from baseline in morning and evening PEF at Week 48 will be analysed separately using similar models as the model for change from baseline in pre-BD FEV1.

The ACQ-6 will be analysed in terms of change from baseline to end of treatment, change from baseline to each of post-randomisation periods, responder status at EOT (i.e. change from baseline to EOT  $\leq -0.5$ ), and asthma symptom control status at EOT (see Section 8.4.3.2 for categorization).

The SGRQ will be analysed in terms of change from baseline to end of treatment, change from baseline to each of post-randomisation periods in total score and three domain scores, and responders as defined by those with a SGRQ total score  $\geq 4$  unit decrease from baseline at EOT.

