Change in mean score from baseline for ACQ-6 and change in total score from baseline for SGRQ (including the domain scores) will be analysed using a similar model as for change from baseline in pre-BD FEV1.

Responder variables for ACQ-6 (yes/no) and SGRQ (yes/no) will be analysed using a logistic regression model with covariates of treatment, region (China/non-China), baseline value, and the use of maintenance oral corticosteroids (yes/no).

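### The ER/hospitalisation exacerbation model does not adjust for prior-year ER or hospital use, although asthma health care use is collected at Visit 1: a small, cheap gain in precision

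*Supplement*

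**What the plan says.** **ER/hospital model.** Section 8.5.2.1 says that the annual rate of exacerbations "associated with an emergency room/urgent care visit or a hospitalization will be analysed using a similar negative binomial model as outlined for the primary" endpoint. It names no covariate specific to this endpoint.

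**Primary model.** Section 8.5.1 lists the terms: "The model will include covariates of treatment group, region (China/non-China), number of exacerbations in the year before the study", plus maintenance oral corticosteroid use, with log follow-up time as offset. There is no eosinophil term.

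**Other models.** The FEV1 repeated-measures model in Section 8.5.2.1 includes baseline FEV1, and the ACQ-6 and SGRQ change scores use a similar model. The ACQ-6 and SGRQ responder models have "covariates of treatment, region (China/non-China), baseline value, and the use of maintenance oral corticosteroids (yes/no" as categories.

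**Data collected.** Section 5.3.3 covers asthma-related health care events: "At Visit 1 Healthcare Resource Utilization (HRU) information will be collected with a 1 year recall period". Section 4.1.1 requires source documents for prior exacerbations and accepts ER, urgent care and hospital records among them. It also states: "Central laboratory tests for absolute blood eosinophil count will be performed at Visit 1".

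**The concern.** Each continuous or responder endpoint above is compared after adjustment for where the patient started on that same measure. The ER/hospital rate is adjusted only for a broader history. Entry requires at least two prior exacerbations (inclusion criterion 7), which compresses the range of that count. The count also cannot distinguish two courses of corticosteroid given in clinic from two admissions.

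A covariate fixed before randomisation that predicts the outcome reduces the variance of the treatment comparison and absorbs chance imbalance. ER/hospital events are likely to be few, so precision is scarce for this endpoint. If the arms differed by chance in prior admissions, an adjustment that was not pre-specified would look post hoc. What is at stake is a little precision on a secondary endpoint outside the gatekeeping procedure of Section 8.5.

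**Working it through.** **Inputs from the protocol.** 222 patients per arm with eosinophils ≥300/µL (Section 8.2), the population for all secondary efficacy endpoints (Section 8.5.2.1); 1:1 allocation (Section 3.3); t = 48×7/365.25 = 0.92 year.

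**The plan's own figure.** The protocol gives no power figure for the ER/hospital endpoint. For the primary endpoint it gives 222 per arm at about 90% power. The assumptions behind that figure are redacted in Section 8.2, so it can only be bracketed. Take the placebo rate of 0.88/year that appears in the amendment history as an assumption, with two-sided 5% and

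n = (1.960 + 1.282)² × [(1/r0 + 1/r1)/t + 2k] / ln(RR)².

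Then 222 per arm corresponds to a dispersion k of 0.39, 1.11 or 2.04 for a rate reduction of 35%, 40% or 45%. The figure is plausible but cannot be confirmed.

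**Assumptions for the ER/hospital endpoint** (none is in the documents): placebo rate 0.1 to 0.2/year, RR 0.5, k = 1.5, and 30% of patients with a prior-year ER/hospital event carrying 2 to 4 times the rate.

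**Simulation** (1,500 trials per scenario, negative binomial maximum likelihood). The ratio is the mean squared SE with the term divided by that without it.

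| Placebo rate/year | Prior-event effect | Variance ratio |
|---|---|---|
| 0.1 | 3× | 0.986 |
| 0.2 | 2× | 0.989 |
| 0.2 | 3× | 0.972 |
| 0.2 | 4× | 0.955 |

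In the 0.2/year, 3× scenario, power goes from 63.0% to 64.7%. A separate simulation (500 trials per setting, 0.1 to 0.2/year, 2 to 3×) gave ratios of 0.97 to 1.00, with or without the prior exacerbation count in the model.

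**Hand check of the 0.2/year, 3× scenario.**
- Mean multiplier: 0.7×1 + 0.3×3 = 1.6. Squared CV: (0.7×1 + 0.3×9)/1.6² − 1 = 0.328.
- Dispersion when the term is left out: 2.5 × 1.328 − 1 = 2.32.
- Variance without the term: [(1/0.2 + 1/0.1)/0.92 + 2×2.32]/222 = 20.94/222 = 0.0943, SE 0.307, power Φ(0.693/0.307 − 1.96) = 61.7%.
- With the term, the information per arm is 222 × Σ share × μ/(1 + 1.5μ). Placebo means are 0.115 and 0.345: 222 × (0.7×0.115/1.173 + 0.3×0.345/1.518) = 30.4. Active means are 0.0575 and 0.1725: 222 × (0.7×0.0575/1.086 + 0.3×0.1725/1.259) = 17.4.
- Variance with the term: 1/30.4 + 1/17.4 = 0.0905, SE 0.301, power 63.4%.

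The variance ratio is 0.0905/0.0943 = 0.96. The approximation is slightly more generous than the fitted models (0.972), but the power gain, just under 2 points, agrees.

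**Cross-check on other assumptions.** With rates of 0.05 to 0.20/year, RR 0.6 and k of 1 to 3, a covariate explaining 30% of the dispersion moves power from 16.4% to 16.5% (0.05/year, k = 1) and from 39.0% to 42.1% (0.20/year, k = 3).

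**Optional eosinophil term in the primary model** (0.88/year, RR 0.6, k = 1.0, SD 0.6 doublings, all assumed). The variance ratio is 0.997, 0.989 or 0.974 if the rate rises 1.15-, 1.3- or 1.5-fold per doubling. In a separate simulation (k = 0.9, 600 trials per setting), a log-rate effect of 0.2 per SD moved power from 91.5% to 92.2%, and 0.4 per SD from 90.0% to 92.3%. The mean rate ratio stayed near 0.60. Under the null, rejection was 4.5 to 5.3% without the term and 4.5 to 5.2% with it.

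**The case against.** **The covariates may be settled elsewhere.** Section 8.5.2.1 calls the model similar, not identical, and no SAP was among the documents reviewed. This stands in part: the SAP may already contain the term. But Sections 8.5.1 and 8.5.2.1 set covariates endpoint by endpoint and signal no different history for this one, so it is worth stating.

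**The existing history is better documented.** The prior exacerbation count is backed by source records and includes events that led to hospitalisation. The Visit 1 utilisation data are broad and rest on recall, and nothing says they were recorded against the ER criterion of Section 5.1.1. That is fair, but a covariate need only be measured before randomisation and be predictive. A yes/no indicator does not have to match the endpoint definition. Overlap with the existing count would shrink the gain, which is why the range starts at zero.

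**Events may be too few.** At 0.1/year and RR 0.5, 222 × 0.92 × 0.1 = 20.4 plus 222 × 0.92 × 0.05 = 10.2 gives about 31 events. Six parameters would become seven, or about 4.4 events each. This stands, and the fix needs a fallback.

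**A stronger reading that does not hold.** A reader might infer that the primary analysis ignores a known prognostic factor, the blood eosinophil count, because Section 1.1.1 speaks of "degree of eosinophilia associated with clinical severity including the risk of asthma exacerbations". That sentence concerns eosinophilic inflammation in the airway. Where the protocol discusses blood counts (Sections 1.1.2 and 1.3), it ties them to the size of the benefit from benralizumab, which is effect modification. Eosinophils are also in use already: for stratification, to define the primary population, and in banded summaries including 300-449 and ≥450/µL. The ≥300/µL restriction narrows the range left for a covariate to explain.

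**Conclusion.** The point holds as a low-severity improvement in efficiency. The ER/hospital exacerbation model carries no history specific to its own kind of event, although data to build one are collected before randomisation and other models in the same section adjust for their own baseline. The expected gain is about 0 to 4.5% in the variance of the log rate ratio, and roughly 2 points of power when a prior event triples a placebo rate of 0.2/year. These figures rest on assumed rates, dispersion, prior-event prevalence and prior-event effect, and on the eCRF allowing asthma ER/urgent care visits and hospitalisations to be identified.

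The plan is not in error. The present model is valid, and the simulations of an added covariate showed no shift in the estimated effect and no inflation of type I error without it. For eosinophils, prognostic value within the ≥300/µL population is an assumption, so the documents support no more than an optional supportive analysis.

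**What to change.** In the SAP, before unblinding (Section 8.1 allows amendments until then):

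1. Add any asthma ER/urgent care visit or hospitalisation in the year before the study (yes/no), taken from the Visit 1 record, to the negative binomial model for ER/hospital exacerbations.
2. Keep the present model as a sensitivity analysis, and name it as the fallback if events are too few to fit the extended model. Write down the rule that triggers the fallback.
3. Optionally, add a supportive version of the primary analysis adjusted for log2 baseline blood eosinophil count. State which value is used when the Visit 1 count was re-tested, since Section 4.1.1 allows one re-test of counts from 150 to below 300/µL. The primary model stays as it is.

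If the sponsor prefers to leave the first term out, a sentence of justification would do. The cost is a few SAP lines and one degree of freedom per extended model, with no new data and no change in sample size.

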#### **8.5.2.2 Analysis methods for safety variables**

AEs will be summarized by means of counts summaries by study period (treatment period and follow-up period). AEs will be listed for each patient and summarized by System Organ Class (SOC) and Preferred Term (PT) assigned to the event by Medical Dictionary for Regulatory Activities (MedDRA). Laboratory safety variables will be summarized using standard

summary statistics and plots as appropriate. Other safety variables will be summarized as appropriate. Further details will be provided in the SAP.

Laboratory data for haematology and clinical chemistry will be summarized. The frequency of changes with respect to normal ranges between baseline and each post-treatment time point will be tabulated. Central laboratory reference ranges will be used for the identification of abnormalities, and a shift table will be produced for each laboratory parameter to display low, normal, high, and missing values. Shifts from normal to abnormal between baseline and post-baseline will be evaluated for urinalysis. Changes in vital signs will be examined at each visit and at endpoint. Baseline to maximum post-baseline and baseline to minimum post-baseline value shift tables will be generated, as applicable for each vital signs parameter. A shift table for ECG will be produced to display the Investigator assessment of normal, abnormal – not clinically significant, abnormal – clinically significant and not done between baseline and end of study. No separate summaries of physical examination findings will be produced since physical examination results will be presented in Medical History and AE summaries.

#### **8.5.2.3 Analysis methods for pharmacokinetic variables**

The PK analyses will be performed at or under the guidance of AstraZeneca Research and Development.

Benralizumab serum concentrations will be summarized using descriptive statistics by visit. Impact of ADA on PK will also be assessed.

The population PK analysis will be presented separately from the main clinical study report (CSR).

#### **8.5.2.4 Analysis method for immunogenicity variables**

Anti-drug antibodies (ADA) to benralizumab will be summarized using descriptive statistics by visit. ADA titers-time profiles of benralizumab by treatment group will be generated. The impact of ADA on PK and eosinophil level will be assessed. The potential association of ADA with safety and efficacy will be evaluated.

### **8.5.3 Subgroup analysis**

To explore the uniformity of the detected overall treatment effect on the primary efficacy variable, subgroup analyses and statistical modeling including testing for interaction between treatment and covariates will be performed in patients with baseline blood eosinophil counts  $\geq 300/\mu\text{L}$  for the following factors: Oral corticosteroids (OCS) use at baseline (yes, no), gender, age (<18, 18 - <65, and  $\geq 65$  years), region (China/non-China), country, BMI ( $\leq 35$ ,  $> 35$   $\text{kg}/\text{m}^2$ ), the number of exacerbations during the previous year (2,  $\geq 3$  exacerbations), the number of exacerbations during medium-high ICS/LABA treatment prior to study enrolment (2,  $\geq 3$  exacerbations), ICS dose at study enrolment (medium, high) and nasal polyps (yes, no). Data will be analysed by negative binomial regression similar to the primary analysis and the same output will be presented for each subgroup as for the primary analysis. For the

statistical modeling including interaction effects, the estimate of the interaction effects will be presented together with the corresponding p-value. These analyses are to be considered as exploratory and will be performed on the full analysis set.

